8.0 Sharing of Results with Subjects*

- 8.1 At the completion of data analysis, we plan to send each participant a short letter outlining study findings and how their participation in the study has helped the hospital. We would like to do this to show the importance of research at Nationwide Children's Hospital.

9.0 Study Timelines

- From enrollment to the last follow-up survey subjects' participation will span 5 months.
- It is estimated to take about 18 months to enroll 450 subjects.

10.0 Inclusion and Exclusion Criteria*

10.1 The study coordinator will screen for eligible patients each morning by checking the census in the EHR of specified behavioral health units. The coordinator will enter the charts of patients that appear to be eligible for the study to determine whether they meet inclusion criteria.

10.2 Inclusion criteria: female adolescents, 14 years and older, admission to the following units – Psychiatric Units (BHP7B and 8A), Youth Crisis Stabilization Unit, Psychiatric Crisis Department Extended Observation Care Unit and patients with mental health disorders admitted to Hospital Pediatrics 3 service awaiting a psychiatric bed/disposition.

Exclusion criteria: wards of state, unable to consent due to mental health disorder, serious medical conditions, non-English speaking, intellectual disability, and known pregnancy.

10.3 Indicate specifically whether you will include or exclude each of the following special populations:

- Individuals who have not yet reached the age of legal consent will be required to complete study consent. We will be submitting the form to waive parental consent for participants 15 and older as the study questions are sensitive and may impede ability to enroll participants with requirements for parental consent. We will require verbal, parental consent for potential participants who are 14 years of age. We will provide the parent or guardian with a study Information Sheet.
- Pregnant women will be excluded from eligibility in the study. However, if a participant becomes pregnant during the study she will not be required to withdraw, as the only study procedures are questionnaires.

11.0 Vulnerable Populations

11.1 This study intends to enroll children, a special population, and will accordingly adhere to additional protections specified under 45 CFR Part 46 Subpart D – Additional Protections for Children Involved as Subjects in Research (45 CFR Part 46.401-409). The study presents no more than minimal risk, we are requesting a waiver of parental consent for participants 15 years and older. For participants that are 14 years old, verbal parental consent will be obtained. In order to facilitate the participation of youth who may not have disclosed diagnosis and treatment of an STD or contraceptive decisions, to remain consistent with standard of clinical care, and to prevent undue conflict or unsafe situations with guardians regarding the nature of these topics, we request a waiver

of parental consent. However, we will be requiring informed consent to be completed by participants as we believe adolescents 14 years of age and older obtain the knowledge and maturity to consent to this study, especially due to the minimal risk associated.

12.0 Local Number of Subjects

- 12.1* It is expected that 450 participants will be recruited for the study.
- 12.2* It is expected that 1,000 adolescents will be eligible for the study from 2021-2023. We estimate that 45% will agree to participate.

13.0 Recruitment Methods

- 13.1* Subjects will be recruited 2021 – 2023. The research coordinator will screen specific inpatient units or services at Nationwide Children’s Hospital as identified by the PI, specifically psychiatric units or units where patients with a mental health diagnosis are generally admitted. Each day the coordinator will screen the hospital census for these units to determine admitted patients that meet inclusion criteria. If there is a question, the research coordinate will confer with the patient’s psychiatric healthcare provider and/or PI. The coordinator will then approach the patient to determine if they are interested in participation. If they express interest, the research coordinator will confirm inclusion/exclusion criteria and then consent the subject.
- 13.2* Patients will be identified through the hospital census, of specified units, for admitted patients. A HIPAA waiver will be completed in order to access minimal information to identify potential participants.
- 13.3* The research coordinator will screen each day from the hospital census of specified units. They will then complete a brief chart review to ensure the patient does meet criteria for the study.
- 13.4* Upon enrollment the subject will be provided with a ClinCard for study compensation. Those who pilot the surveys will receive a one-time compensation of \$20. For those enrolled in the full study, at the time of completion of the enrollment survey \$50 will be added to the card. At the time of completion of the two subsequent follow-up surveys \$25 will be added for each survey. Subjects can earn up to \$100 for their participation. The study is externally funded by Merck.

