6.0 Procedures Involved*

6.1 This is an observational study. The study components include participant surveys, EHR data extracts related to sexual and reproductive health, and statistical process control charts for quality improvement analyses. Three surveys will be administered to participants, the first at the time of enrollment, the second immediately after discharge, and the third four months after discharge.

6.2 Potential participants will be approached during their admission at NCH and invited to participate in the study. If they are interested in participation, they will complete an electronic informed consent via redcap, all study participants will receive a copy of their consent via e-mail. If the participant is 14 years old the coordinator will be required to obtain verbal consent from the parent or guardian via Information Sheet. After the consent process is completed, they will fill out the first study survey while they are admitted to the hospital (see Appendix A). The

PROTOCOL TITLE: Evaluation of Contraception Care @ Behavioral Health Pavilion

subsequent two surveys will be sent electronically via their preferred communication method, which will be determined at enrollment. After the last survey is completed the subject will have completed their portion of the study. This is a study with adolescents as the study population and there will be little parental involvement, there are concerns regarding study retention. We will be providing texts as a communication option for the participants as we believe this will be most successful. If a participant chooses this as their preferred contact method. In order to text participants, we will be utilizing Twilio, an NCH approved application.

Study staff will review responses on the following questions on the baseline survey: if the participant indicates they would like to a) learn more about, b) initiate or change contraception methods, and c) desire for privacy for contraception care. Study staff will notify the patient's clinical team if any of these are positive.

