On the day of discharge, or the first business day after discharge if participant is discharged during the weekend or a holiday, study staff will send the second survey (see Appendix B) to the participants who indicated interest in contraception counseling and initiation via their preferred communication method. The patient will have 1 month to complete the survey. They will receive weekly reminders if the survey is incomplete, and after 1 month the participant will be considered lost to follow up for the first follow-up survey. The third survey (see Appendix C) will be sent to the participants who indicated interest in contraception counseling and initiation 4 months after the patient is discharged from the hospital. Again, the participant will be provided the survey link via their preferred contact method and given 1 month to complete the survey and study staff will provide weekly reminders until completion. Completion of the third survey indicates the patient has completed their portion of the study. After 1 month, if the third survey is incomplete, the patient will be considered lost to follow up.

Additionally, routine data pulls from the electronic health record (EHR) will be generated to gather supplementary data not collected from the subject surveys (see Appendix D).

To ensure optimal readability, prior to the start of the enrollment period for the study we will be sending the surveys through the health literacy department. We will also pilot the surveys to 10-15 adolescent patients, ages 14 years and older, we would like to do this in order to get feedback on survey design, so that we can make necessary changes before enrollment starts. These patients may be approached in the Adolescent Medicine Clinic or may be children of NCH employees or other colleagues.

6.3 We do not anticipate any risks associated with enrollment in the study. All PHI and sensitive information recorded for research will only be available to study staff. Additionally, we will be requesting waived parental consent for participants 15 and older to mitigate any potential conflict between parent and participant due to the sensitive nature of this

study. Please see appendices A, B, and C and D for survey and data collection forms.

6.4 Once a participant enrolls in the study, they will then be prompted to complete the baseline survey (Appendix A).

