17.0 Data Management* and Confidentiality

17.1 *Describe the data analysis plan, including any statistical procedures or power analysis.*

For our first objective, the dependent variables are interest in receiving contraception counseling during a hospital stay and interest in starting a contraceptive during a hospital stay.

- We will examine interest in receiving contraception counseling during hospitalization among female adolescents hospitalized with mental health disorders by assessing the proportion of participants who answer yes to the following survey question “Interest in learning more about contraception during your hospital stay”.
- We will examine interest in initiating contraception during hospitalization among female adolescents hospitalized with mental disorders by assessing the proportion of participants who answer yes to the following question “Interest in starting a contraceptive during your hospital stay”.
- We will perform univariate descriptive analyses on all variables.
- We will perform bivariate analysis to explore the relationship between variables “Interest in learning more about contraception during your hospital stay” and “Interest in starting a contraceptive during your hospital stay” using 2 X 2 contingency tables.

PROTOCOL TITLE: Evaluation of Contraception Care @ Behavioral Health Pavilion

- We will explore associations with dependent variables and predictor variables by performing bivariate analyses of “Interest in learning more about contraception during your hospital stay” and “Interest in starting a contraceptive during your hospital stay” with predictor variables from surveys and EHR variables using Chi square for categorical variables and Students T-test for continuous variables.
- We will regress significant predictor variables ($p < 0.1$) on dependent variables to determine predictors of “interest in receiving contraception counseling during your hospital stay” and “interest in starting a contraceptive during your hospital stay”.

For our second objective the dependent variables are contraceptive prescription/initiation during hospitalization and contraceptive prescription/initiation following discharge.

- We will create derived variables:
 - Initiation any contraceptive (in hospital, in BC4Teens clinic, none)
 - Initiation preferred contraceptive (in hospital, in BC4Teens clinic, none)
 - Time interval (days) between enrollment and contraception prescription/initiation

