20.0 Consent Process

20.1 Indicate whether you will you be obtaining consent, and if so describe:

- The consent process will take place at the patient's bedside during their admission.
- After reviewing the consent with the subject, the research coordinator will ask if they have any questions. There will not be an official waiting period; however, if they would like time to think about participation that will be granted.
- When a participant indicates they would like to learn more about the study, informed consent will be reviewed with the subject by the research coordinator. Potential participants will be educated on the purpose of the study as well as any risks or benefits associated with their participation. The informed consent will contain all study processes as well as the measures that will be taken to ensure any data collected will be kept confidential. They will also be made aware that they can discontinue their participation at any time as research is completely voluntary.
- This study is important because little is known about the sexual and reproductive healthcare needs of female adolescents with mental health disorders. The principle of justice supports the

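### As written, half of the $100 payment is open only to participants who indicate interest in contraception at baseline, which may put an upward incentive on the first primary endpoint

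*Combined protocol and SAP*

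**What the plan says.** **Payment (Section 13.4).** For the enrollment survey, "at the time of completion of the enrollment survey \$50 will be added to the card". Then "At the time of completion of the two subsequent follow-up surveys \$25 will be added for each survey. Subjects can earn up to \$100", with no restriction attached to that ceiling.

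**Who gets the follow-up surveys.** In Section 6.2, "study staff will send the second survey (see Appendix B) to the participants who indicated interest in contraception counseling and initiation". The same condition is set there for the third survey, four months after discharge. Section 6.4 repeats the condition but joins counseling and initiation with *or* where Section 6.2 has *and*.

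**Text without the condition.** Section 6.1 says "Three surveys will be administered to participants, the first at the time of enrollment" and goes on to the other two surveys without limiting who receives them. Sections 1.0 and 9.0 give 5 months of participation per subject, again without a limit.

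**Outcome (Section 17.1).** The first objective is analyzed by "assessing the proportion of participants who answer yes to the following survey question", once for interest in learning about contraception and once for interest in starting it, both during the hospital stay. Section 23.1 says that interest of at least 25% would be notable.

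**Consent (Sections 6.2 and 20.1).** Consent comes before the baseline survey, and "The informed consent will contain all study processes".

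**The concern.** The answers that define a primary endpoint also appear to decide whether a participant can earn the second $50. If she knows this before she answers, the payment rule gives her a reason to say yes that has nothing to do with interest in contraception. A larger sample would not remove such a bias, and no planned analysis addresses it.

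Two results are exposed: the proportion reporting interest, and the Section 17.1 analysis of initiation among participants interested in contraception care, whose denominator would take in any insincere yes. Initiation among all participants has a different denominator and is not affected in this way.

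The wording conflict decides which answer opens the payment. Under *and*, a yes to learning alone earns nothing extra, and the incentive is to say yes to both items. Under *or*, a single yes is enough.

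**Working it through.** **The plan's own figures.** Maximum payment: 50 + 2 × 25 = $100, as stated in Section 13.4. Sample size: 1,000 × 0.45 = 450, as stated in Section 12.0. Section 2.2 gives no hypothesis and the documents give no alpha or power, so there is no power figure to reproduce.

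**Payment by baseline answer**, reading Sections 6.2, 6.4 and 13.4 literally:

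- No interest indicated: $50.
- Interest indicated: $50 + 2 × $25 = $100, if both follow-up surveys are completed.
- Share of the maximum that depends on the answer: 50/100 = 50%.

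**Possible effect on reported interest.** Let p be true interest and f the share of uninterested participants who answer yes. Both are assumed; the documents give neither. Observed interest = p + f(1 − p). With p = 20%:

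| f | Observed interest | Bias (points) |
|---|---|---|
| 2% | 0.20 + 0.02 × 0.80 = 21.6% | 1.6 |
| 5% | 0.20 + 0.05 × 0.80 = 24.0% | 4.0 |
| 10% | 0.20 + 0.10 × 0.80 = 28.0% | 8.0 |

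**Scale.** The 95% half-width at 25% is 1.96 × √(0.25 × 0.75 / 450) = 0.040, or 4.0 points. At p = 20%, a false-yes rate of 5% gives a bias of the same size.

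**Against the 25% mark.** 0.25 × 450 = 112.5, so at least 113 yes answers are needed. With p = 20%, the binomial chance of 113 or more is 0.5% at f = 0, 31% at f = 5% and 92% at f = 10%. The f that brings the expected proportion to 25% is (0.25 − p)/(1 − p):

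- p = 22%: f = 3.8%, about 14 false yeses among 450.
- p = 20%: f = 6.25%, about 23.
- p = 15%: f = 11.8%, 45.
- p = 10%: f = 16.7%, about 68.

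**Initiation among the interested.** If no false-yes participant initiates (assumed), the reported proportion is the true one multiplied by p/[p + f(1 − p)]. With p = 20% this is 0.20/0.216 = 0.93 at f = 2%, 0.20/0.24 = 0.83 at f = 5% and 0.20/0.28 = 0.71 at f = 10%.

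**The case against.** A reader might infer that the reported proportion will be inflated. The documents do not support that, for these reasons:

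- **Knowledge of the rule.** The incentive works only if a participant knows the condition and connects it to payment before she answers. The general statement in Section 20.1 makes this plausible, but the consent form is not in the documents.
- **The money is for work.** The second $50 is paid for completing two further surveys, one after discharge and one four months later. It is not paid for the answer itself.
- **Pressure the other way.** Under Section 6.2 a positive answer is passed to the clinical team. Section 15.1 names the risk of a parent or guardian learning of participation. Either could deter a false yes or suppress a true one.
- **An unsettled condition.** Sections 1.0, 6.1, 9.0 and 13.4 read as though everyone is followed, and Sections 6.2 and 6.4 disagree on *and* versus *or*. Appendix A is not in the reviewed text, so the exact items that open follow-up cannot be checked against the two outcome questions.

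These points stand. They limit what can be said about size and net direction. They do not remove the payment difference, because nothing in the protocol gives uninterested participants equal payment or says that the condition is concealed. The last point is itself a reason to amend the text.

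**Conclusion.** The point holds as a design weakness. Read literally, the plan caps a participant who indicates no interest at $50 and one who indicates interest at $100, and the interest answers are a primary endpoint. Payment taken alone can only favor a yes, provided that participants know the rule. Whether the reported proportion ends up too high, and by how much, cannot be determined from the documents.

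The illustrative figures rest on assumed values of p and f. They show that a modest false-yes rate could match the sampling error or carry the estimate past 25%; they do not show that this is likely. It would also be too strong to say that the second primary objective as a whole is compromised, since only the analysis restricted to interested participants would be diluted. The incentive is avoidable at modest cost and should be removed.

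**What to change.** Reconcile Sections 6.2 and 6.4 with each other and with Sections 1.0, 6.1, 9.0 and 13.4: send surveys 2 and 3 to all enrolled participants at the same $25 each, and skip items that do not apply to those who did not indicate interest. State in the consent that follow-up and payment do not depend on any survey answer.

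**Cost.** A protocol and consent amendment, and more post-discharge messages to uninterested participants, which bears on the parental-discovery risk in Section 15.1. If 25% are interested (assumed; 113 of 450) and every survey is completed, payments rise from 450 × $50 + 113 × $50 = $28,150 to 450 × $100 = $45,000. The increase is 337 × $50 = $16,850, within the stated $100 per subject.

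**If the budget is fixed.** Use smaller payments with the same maximum for everyone. On the same assumption that is 28,150/450, or about $62 each, at the price of a weaker incentive per survey.

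**For participants already enrolled under the present rule.** Report the payment rule as a limitation of the interest proportion.

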14.0 Withdrawal of Subjects*

- 14.1* Participation in the study is always voluntary, so subjects can decide to withdraw at any time by notifying the research coordinator. There are no instances that would require the study team to withdraw a subject as there are no risks to participating in the study.
- 14.2* Describe any procedures for orderly termination: N/A

14.3 If a subject decides they would like to withdraw they will receive no further contact from study staff, this includes follow-up surveys as well as the memo at study completion. Any data collected prior to the withdraw will be kept and de-identified to protect the subject, unless they request all of their information be removed from the study.

15.0 Risks to Subjects*

15.1 There is minimal risk associated with this study. There is a risk of the subject's parent or guardian learning of the subject's participation in the study. Additionally, the study surveys do ask some sensitive information; to mitigate any discomfort they may be associated with these questions we will be requesting to waive parental consent, so that the subject is more comfortable participating in the study.

16.0 Potential Benefits to Subjects*

16.1 It is important for researchers and clinicians to better understand the sexual and reproductive healthcare needs of adolescents with mental health disorders, an area that has received little research and clinical interest. Adolescents, themselves, will benefit as care protocols are informed with scientific evidence derived from researching them directly.

17.0 Data Management* and Confidentiality

17.1 *Describe the data analysis plan, including any statistical procedures or power analysis.*

For our first objective, the dependent variables are interest in receiving contraception counseling during a hospital stay and interest in starting a contraceptive during a hospital stay.

- We will examine interest in receiving contraception counseling during hospitalization among female adolescents hospitalized with mental health disorders by assessing the proportion of participants who answer yes to the following survey question “Interest in learning more about contraception during your hospital stay”.
- We will examine interest in initiating contraception during hospitalization among female adolescents hospitalized with mental disorders by assessing the proportion of participants who answer yes to the following question “Interest in starting a contraceptive during your hospital stay”.
- We will perform univariate descriptive analyses on all variables.
- We will perform bivariate analysis to explore the relationship between variables “Interest in learning more about contraception during your hospital stay” and “Interest in starting a contraceptive during your hospital stay” using 2 X 2 contingency tables.

PROTOCOL TITLE: Evaluation of Contraception Care @ Behavioral Health Pavilion

- We will explore associations with dependent variables and predictor variables by performing bivariate analyses of “Interest in learning more about contraception during your hospital stay” and “Interest in starting a contraceptive during your hospital stay” with predictor variables from surveys and EHR variables using Chi square for categorical variables and Students T-test for continuous variables.
- We will regress significant predictor variables ($p < 0.1$) on dependent variables to determine predictors of “interest in receiving contraception counseling during your hospital stay” and “interest in starting a contraceptive during your hospital stay”.

For our second objective the dependent variables are contraceptive prescription/initiation during hospitalization and contraceptive prescription/initiation following discharge.

- We will create derived variables:
 - Initiation any contraceptive (in hospital, in BC4Teens clinic, none)
 - Initiation preferred contraceptive (in hospital, in BC4Teens clinic, none)
 - Time interval (days) between enrollment and contraception prescription/initiation
 - Initiation of contraceptive not preferred contraceptive (in hospital, in BC4Teens)
- We will perform univariate descriptive analyses on all variables.
- We will examine contraception initiation all among participants by assessing the proportion of participants who initiate any contraceptive in the a) hospital setting, b) in BC4Teens clinic, and c) either hospital or BC4Teens clinic.
- We will examine contraception initiation all among participants by assessing the proportion of participants interested in contraception care who initiate any contraceptive in the a) hospital setting, b) in BC4Teens clinic, and c) either hospital or BC4Teens clinic.
- We will examine how time between enrollment and Initiation any contraceptive varies by location of contraception prescribing/initiation using Student’s T test.
- We will also perform the 3 analyses above on the variable “initiate preferred contraceptive”
- We will examine the type of contraceptive method prescribed/initiated in the a) hospital setting, b) in the BC4Teens clinic setting, and c) either hospital or BC4Teens clinic
- We will examine variation in type of contraceptive method prescribed/initiated between the hospital setting and the BC4Teens clinic setting using Chi square.
- We will explore associations with dependent variables and predictor variables by performing bivariate analyses of “initiation

PROTOCOL TITLE: Evaluation of Contraception Care @ Behavioral Health Pavilion

any contraceptive” and predictor variables from surveys and EHR variables using Chi square for categorical variables and Students T-test for continuous variables.

- We will regress significant predictor variables ($p < 0.1$) on dependent variables to determine predictors of initiation any contraceptive.
- To better understand personal and system-level differences in initiation of contraception during hospitalization and in BC4Teens clinic, we will examine differences in demographics, survey variables of interest, and EHR variables of interest between participants who initiate “any contraceptive during hospitalization” and initiate “any contraceptive in BC4Teens clinic” using Chi square.
- To better understand personal and system-level differences in initiation of preferred contraceptive and not-preferred contraceptive we will examine differences in demographics, survey variables of interest, and EHR variables of interest between participants who initiate “preferred contraceptive” and initiate “not preferred contraceptive” using Chi square.
- Statistical process control methods will be used to evaluate trends in contraceptive contraception counseling for hospitalized female adolescents with mental health disorders.
- Statistical process control methods will be used to evaluate trends in contraceptive initiation for hospitalized female adolescents with mental health disorders.
- Statistical process control methods will be used to evaluate trends in initiation of contraceptive implant for hospitalized female adolescents with mental health disorders.

17.2 The enrollment survey as well as follow-up surveys will be collected in RedCap. The database is a secure data management platform that only study staff will have access to. When the data is exported it will all be de-identified. Additionally, there will be quarterly data pulls to gather additional patient information. The data will be stored on a password-protected spreadsheet that only study staff have access to. At the completion of data collection the spreadsheet will be de-identified for purposes of analysis. At this time, the only PHI will be stored on an enrollment log to serve as a master list of all participants, this will also be password protected with access only provided to the study staff.

17.3 *Describe any procedures that will be used for quality control of collected data.*

- When enrollment begins the EHR data will be gathered more frequently to ensure that the process is obtaining accurate information. During this time the coordinator will

also do manual chart reviews to ensure the data reports are providing the same information. As the study progresses the data extraction will occur less frequently; however, the study coordinator will be required to chart review 5 patients to ensure the data is still intact.

17.4 Describe how data will be handled study-wide:

- During data collection surveys will be stored within RedCap, a secure data management platform. The data pull variables will be kept in a password protected excel spreadsheet. Once the data collected period is over the RedCap data will be merged onto the password protected spreadsheet. At this time the data will be de-identified and a separate participant master list containing PHI will be kept separately. Only study staff will have access to the PHI.
- Data will be stored for three years after the data collection period is complete, this will allow for data analysis to take place.
- Only study staff included on the IRB will have access to the data. When the data is analyzed and given to the biostatistician it will be completely de-identified.
- OSU staff associated with the study will receive study reports. The data will be transmitted via secure transfer through approved electronical modalities. NCH study staff will be responsible for ensuring all data is de-identified prior to sending as well as ensuring secure transfer is successful.
- The sponsor, Merck, has requested quarterly reports as a part of this study. Data transfer will occur electronically through Merck's grant management website. Any study subject level data will be coded with a number and no PHI will be included.

